[name]	Protocol development, research methodology, research background, dissemination, patient and public involvement strategy	
[name]	Protocol development, research methodology, background, dissemination, patient and public involvement strategy	
[name]	Protocol development, research methodology, dissemination	
[name]	Research methodology, development of health economics	
[name]	Research methodology, development of statistical approach	
[name]	Protocol development, research methodology, research background, dissemination	
[name]	Patient and public involvement strategy	

STIM-STROKE Protocol v1.0 30-04-2025

IRAS ID: 332116 Page **13** of **70**

viii. KEY WORDS

Stroke, electrical stimulation, motor recovery, lower limb,

ix. TRIAL FLOW CHART

Patient flow through the trial is described in Figure 1 below.

Figure 1 Trial Flow Chart

STIM-STROKE Protocol v1.0 30-04-2025

IRAS ID: 332116 Page **14** of **70**

Screening and Consent

Patients within two weeks of stroke will be screened by research practitioner and therapy team for eligibility (> 18 y/o, within 2-weeks of stroke, NIHSS score of ≥ 3 for the lower limb, unable to walk (with or without AD).

Patients that meet the eligibility criteria will be provided with a PIS and study introduction.

Informed consent or consultee consent will be obtained for those that want to take part.

Do not meet eligibility criteria or decline to participate (reason logged with permission)

NIHSS- National Institute of Health Stroke Scale

AD- assistive device

MRS - Modified Rankin Scale

NPRS – Numerical Pain Rating Scale

VAS – Visual Analogue Scale (pain)

[figure not shown]
30 SCSST – 30 Second Chair Sit-Stand Test

EQ-5D-5L - EuroQOL

SNMES- surface neuromuscular electrical stimulation

Baseline Assessment (Visit 1)

Demographic and stroke information, Trunk Control Test, MRS, NPRS, VAS< dynamometer (strength), limb circumference, 30 SCSST, EQ-5D-5L, Barthel Index, Nottingham Sensory Assessment.

Visit 2, 6 weeks Follow up

Dynamometer (strength), limb circumference, 30 SCSST, EQ-5D-5L, NPRS, VAS, Barthel Index, Nottingham Sensory Assessment, resource use questionnaire

Visit 3, 12 week Follow up

Dynamometer (strength), limb circumference, 30 SCSST, EQ-5D-5L, NPRS, VAS, Barthel Index, Nottingham Sensory Assessment, 10 Metre Walk Test, resource use questionnaire. SNMES group return stimulators.

Visit 4, 6 month Follow up - END OF STUDY

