1.1. Assessment and management of risk

Electrical stimulation is currently being used in routine care physiotherapy practice with minimal reports of adverse events. Electrical stimulation has been incorporated into best practice guidelines for people with stroke as well as people with Multiple Sclerosis. The risk associated with using electrical stimulation within this study is not different to using electrical stimulation within routine clinical practice.

Previous study of electrical stimulation report few adverse events. Common adverse events when they occur are skin irritation at the electrode site, muscle fatigue and soreness following electrical stimulation and joint pain.

Participants will be instructed to let the research team know if they experience any adverse events, these will be monitored as per Section 8 Safety Measures. If participants experience muscle soreness, muscle fatigue, joint pain, or skin irritation they will be supported by the research team to manage this to be able to continue in the study.

The benefits of using electrical stimulation are maintaining muscle bulk and size which will help to prevent atrophy, improved circulation at the stimulation site, and the time doing the stimulation will contribute to additional minutes of exercise which is recommended in the new Clinical Stroke Guidelines.

2. OBJECTIVES AND OUTCOME MEASURES/ENDPOINTS 2.1. Primary objective

The primary aims of this feasibility study are to i. assess the feasibility and acceptability of SNMES started within 2-weeks after stroke and applied for 12-weeks to the weakened lower limb muscles and ii.to provide necessary data to inform the design of a future definitive RCT testing whether SNMES started within two weeks after stroke prevents muscle wastage and improves recovery of strength, walking and quality of life in people with severe lower extremity weakness.

The primary feasibility and acceptability objectives are described below.

- 1. Determine the feasibility and acceptability of the SNMES intervention started within 2-weeks in people after stroke.
- 2. Estimate screening, recruitment and attrition rates, and reasons for declining participation or leaving the study early (where possible).
- 3. Estimate adherence/engagement to the SNMES protocol, including number of sessions completed/total sessions in treatment protocol

STIM-STROKE Protocol v1.0 30-04-2025

IRAS ID: 332116 Page **17** of **70**

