5. TRIAL PROCEDURES

Following completion of the baseline measures, individual participant randomisation will take place. Participants will be randomised to either the intervention group to receive SNMES alongside their usual care or to the control group to receive usual care alone. Participants in both groups will continue to receive their usual care and both will take part in study assessments.

Intervention group

SNMES treatment will be started within two weeks of stroke, and within 4 days of randomisation, to account for randomisation on a Friday and starting the intervention the following week. SNMES will be targeting only the weakened stroke-affected leg muscles of the thigh (hamstring, quadriceps, triceps surae) and calf (anterior tibialis, gastroc soleus). The SNMES intervention will be delivered alongside and in addition to usual care.

Treatment with SNMES is provided using a commercial constant current 2-channel battery operated electrical stimulation device and is designed in line with previous evience. ¹³

Participants receiving SNMES will be provided with

- SNMES stimulator unit
- Knee immobiliser brace
- Ankle foot orthosis

STIM-STROKE Protocol v1.0 30-04-2025

IRAS ID: 332116 Page **24** of **70**

- 4 large electrode pads
- 4 small electrode pads
- An extra 9 volt battery
- SNMES diary (in the format of their choice, written or digital)

The treating clinician will teach the participant and their family/caregivers how to use the knee and ankle braces, apply the electrodes, set up the stimulator, carry out stimulation, remove the electrode pads, and storage of the electrode pads and stimulation devices. Participants and caregivers will be provided with an instructional booklet containing written information and videos about how to use the electrical stimulation unit, electrodes, trouble shooting, and when to stop electrical stimulation. Participants and caregivers will also be provided with a diary to track their stimulation sessions and reasons for not doing a session.

The general procedure that will be used on each muscle/joint is described below.

[figure not shown]
- 1. The motor points for the appropriate muscle will be identified by the therapist. The therapist will mark this spot on the skin with a permanent marker for future sessions. This will help to ensure consistent stimulation.
- 2. The gel electrode is placed on the muscle motor point of the weak leg (stroke affected leg). Please see the images below.

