STIM-STROKE Protocol v1.0 30-04-2025

[figure not shown]
IRAS ID: 332116 Page **25** of **70**

This picture demonstrates electrode placement on the muscles of the thigh. The picture on the left is the anterior thigh muscles (quadriceps) and the picture on the right is the posterior leg muscles the hamstrings.

This picture demonstrates electrode placement on the muscles of the calf. The picture on the left is the anterior thigh muscles, the anterior tibialis and the picture on the right is the posterior leg muscles the gastrocnemius and soleus.

- 3. The stimulator leads are connected to electrodes.
- 4. For participants using the braces, the limb is positioned into a standard lower limb (thigh and calf) brace/splint and ankle foot orthosis (AFO) in a comfortable position. This is to prevent limb movement during the stimulation. Use of the brace will be optional, depending on patient preference and achieving a good limb position.
- 5. The stimulator is turned on and programmed at the following settings:
 - a. Frequency of 50Hz
 - b. Pulse duration: 450 µs
 - c. ON:OFF time: 5:10 seconds

STIM-STROKE Protocol v1.0 30-04-2025

IRAS ID: 332116 Page **26** of **70**

- d. Intensity is increased until a visible muscle contraction (this is when you can see the muscle move and contract) is produced of the muscle of interest. The intensity is then increased to participant tolerance. The intensity is determined at each individual session.
- 6. Each muscle will be stimulated for 45 contractions, this is around 30 minutes in total for all four leg muscles (12 minutes for the thigh, 12 minutes for the calf, and 6 minutes for attaching the stimulator to the electrodes and for programming the session).
- 7. When the stimulation is complete the stimulator leads are removed from the electrodes.
- 8. The electrodes are removed from the skin and stored in their packaging for the next session.
- 9. The stimulator and electrode leads are stored in the stimulator box until the next session

This process is repeated for each muscle group (quads/hamstring, gastroc soleus/anterior tibilais).

SNMES will be carried out three times a week for 12 weeks.

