All participants will complete follow up assessments at 6-weeks (Visit 2), 12-weeks (Visit 3) and 6 months (Visit 4) after randomisation. These assessments will be administered by research practitioners and take place at the trust in which the participant was admitted for their stroke (UDH or the second site). If the participant is not able to walk or completes transfers by hoist the assessment can be carried out in the community at their place of residence. Research team members that undertake assessments in the participant's place of residence and will follow lone working policies associated with the trust.

Follow up Assessments

A summary of the study baseline and follow up assessments are in Section 5.5 and 5.6 as well as in Table 2 in Section 5.6.

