5.6. Trial assessments

Trial assessments will take place at baseline (Visit 1), 6-weeks after baseline (visit 2), 12-weeks after baseline (Visit 3), and 6-months after baseline (Visit 4). Please refer to Table 2 below for details regarding what data is collected at each visit.

Data at each visit will be collected by the research practitioner who is trained in carrying out each assessment and is documented in the delegation log.

The assessment window for Visit 2 is +/- 3 days to account for the weekend in which research practitioners would not be working. The assessment window for Visit 3 and visit 4 is +/- 7 working days. It is not expected that at Visit 3 or Visit 4 there will be rapid changes in function thus the longer assessment window.

Please see Appendix 3 for complete details and instructions for how to complete each assessment.

STIM-STROKE Protocol v1.0 30-04-2025

IRAS ID: 332116 Page **39** of **70**

Table 2 Schedule and Rationale of Assessments

Measure	Brief Description	Screening	Visit 1 (baseline)	Visit 2 (6- weeks) (+/- 3 days)	Visit 3 (12 - weeks) (+/- 7 days)	Visit 4 (6 months) (+/- 7 days)
NIH Stroke Scale (NIHSS)	Assess leg strength and ability of the stroke affected leg.	Х				
Trunk Control Test (unsupported sit)	Assesses trunk control, trunk strength, and unsupported sitting balance. There is evidence that better trunk control/sitting balance is associated with return to walking.		Х			
Walking ability	Assessment of if the person can walk without support. Participants will be included if they need support and help to walk.	Х				
Modified Rankin Scale	Assesses function and ability/disability after stroke.		Х			
Numerical Pain Rating Scale	Assessment of pain, rating scale from 0 no pain to 10 extreme pain in the stroke affected leg.		Х	X	Х	Х

Measure	Brief Description	Screening	Visit 1 (baseline)	Visit 2 (6- weeks)	Visit 3 (12 - weeks)	Visit 4 (6 months)
				(+/- 3 days)	(+/- 7 days)	(+/- 7 days)
Dynamometer	Assess the strength of muscles of the thigh and calf (Quadriceps, hamstrings, gastroc soleus, and anterior tibialis).		Х	Х	Х	Х
Oxford Grading Scale/Medical Research Council Scale	Measure of strength of the lower limb rating from 0/5 no muscle activity to 5/5 full strength against resistance.		Х	Х	Х	Х
30 second chair sit-stand test	Number of sit-to stands and stand-to sits in 30 seconds, this assesses functional ability, lower extremity muscle power, and muscles endurance.		Х	Х	X	Х

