Qualitative data from participants with stroke, caregivers, and clinicians will be analysed separately and where appropriate, we will synthesise experiences ensuring the recognition of the respective group voices. Findings will be mapped to the TFA and be used to inform study strategies for facilitating recruitment, retention, adherence and communication in a future trial.

Feasibility progression criteria

RAG (Red/amber/green) progression criteria ⁵⁰ will be used to assess the key feasibility objectives of recruitment, intervention adherence and retention to inform whether a main trial is possible and whether aspects of the design or other issues need modification in order to conduct the research successfully (Table 3).

Process data will be used to describe interpreted timelines to identify "fixable", "manageable" and "insurmountable" challenges to site opening, training, data collection and intervention fidelity, with regard to both the future main trial and clinical implementation in the event of a positive trial.

Table 3 RAG Criteria for Study Progression

STIM-STROKE Protocol v1.0 30-04-2025

IRAS ID: 332116 Page **55** of **70**

Outcome Green		Amber	Red
	(feasible with minimal or no modifications)	(feasible with moderate modification)	(major modification required, limited feasibility)
Recruitment	≥ 50 participants	30-49 participants	< 30 participants
(target n=60) Incomplete follow up	< 20%	20-40%	>40%
at 6 months Intervention	≥75%	50-75%	<50%
adherence	(≥27 sessions completed)	(18-26 sessions completed)	(<18 sessions completed)

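### Visit 3 is timed from baseline or randomisation with a two-sided window, so an early visit can fall before the 12-week SNMES course ends while adherence is still scored against 36 sessions

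*Protocol*

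**What the plan says.** **Course and start.** Section 5 of the protocol says "SNMES will be carried out three times a week for 12 weeks". Treatment is to begin "within 4 days of randomisation, to account for randomisation on a Friday and starting the intervention the following week".

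**Visit 3 anchor.** Section 5 places the follow-up visits at "12-weeks (Visit 3) and 6 months (Visit 4) after randomisation" (with Visit 2 at 6 weeks). Section 5.6 counts the same visits from baseline. Neither counts from the first SNMES session.

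**Visit 3 window.** The text of Section 5.6 says "The assessment window for Visit 3 and visit 4 is +/- 7 working days". The column headings of Table 2 give plus or minus 7 days, without the word working.

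**Stimulator return.** The flow chart entry for Visit 3 says "SNMES group return stimulators". The discharge paragraph of Section 5 instead has the device come back on completion of the intervention and names no visit.

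**Adherence.** Section 2.1 defines it as "number of sessions completed/total sessions in treatment protocol". Table 3 in Section 7.3 sets Green at 75% or more ("≥27 sessions completed") and Amber at 50 to 75% ("18-26 sessions completed").

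**The concern.** Adherence is one of the three progression criteria, and its denominator is the full course. The visit that closes the treatment period is tied to a date that does not move with the start of treatment, and it may be held early. If the device is handed back at an early Visit 3, the last sessions cannot take place, yet they remain in the denominator. This bias runs in one direction only: visit scheduling can lower measured adherence but cannot raise it. Section 2.3 uses the adherence data to judge whether the suggested dose is feasible on a larger scale, so a shortfall caused by the calendar could be read as a shortfall in engagement.

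The protocol appears to intend Visit 3 to mark the end of the course. Section 5.8 places the stroke participants' interviews after the 12-week intervention is complete, and Table 2 schedules them at Visit 3. A window that opens before the course ends does not serve that intent.

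**Working it through.** **1. The plan's own figures.** 3 sessions per week × 12 weeks = 36. Green: 0.75 × 36 = 27. Amber floor: 0.50 × 36 = 18. Both match Table 3, so the criterion is scored against 36.

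**2. Inputs.** Course length 84 days from the first session; start 0 to 4 days after randomisation (Section 5); Visit 3 target 84 days after randomisation (Section 5); early limit 7 working days (Section 5.6 text) or 7 calendar days (Table 2).

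**3. Assumptions that the protocol does not fix.** Randomisation and first session fall on weekdays. Baseline is on the day of randomisation. Sessions fall on days 0, 2 and 4 of each treatment week, with no catch-up. The stimulator is returned at Visit 3. Bank holidays are ignored.

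**4. How early Visit 3 can be.** Gap to the end of the course = calendar days before target + start delay.

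- Seven working days is 9 calendar days if the target is a Wednesday, Thursday or Friday, and 11 if it is a Monday or Tuesday.
- Text window: shortest gap 9 + 0 = 9 days; longest 11 + 4 = 15 days (randomised Monday, started Friday).
- Table 2 window: 7 + 0 = 7 to 7 + 4 = 11 days.
- The protocol's own example, randomisation on a Friday and a start on Monday or Tuesday: 9 + 3 = 12 or 9 + 4 = 13 days under the text window.

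**5. Sessions that fit before the visit.** Visit day counted from the first session = 84 − gap.

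- Gap 15: visit on day 69. Nine full weeks give 27 sessions; days 63, 65 and 67 add 3, making 30.
- Gap 9: visit on day 75. Ten full weeks give 30; days 70, 72 and 74 add 3, making 33.
- Gap 11 (Table 2): visit on day 73. Ten full weeks give 30; days 70 and 72 add 2, making 32.
- Gap 7 (Table 2): visit on day 77. Eleven full weeks give 33 (34 if a session on the visit day counts).
- Visit 3 exactly on target, counting a session on that day: 36 with a start 0 to 3 days after randomisation, 35 with a day-4 start.

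| Visit 3 timing | Days before course ends | Sessions available | Share of 36 | Share of available needed for 27 |
|---|---|---|---|---|
| Early limit, text window | 9 to 15 | 30 to 33 | 83% to 92% | 90% to 82% |
| Early limit, Table 2 window | 7 to 11 | 32 to 33 | 89% to 92% | 84% to 82% |
| Nominal date | 0 to 4 | 35 to 36 | 97% to 100% | 77% to 75% |

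**6. Effect on the criterion.** At 30 available sessions, the allowance for missed sessions within Green falls from 36 − 27 = 9 to 30 − 27 = 3. A participant who completes 75% of those 30 has 22.5 sessions, scored as 22.5/36 = 62.5%, which is in the Amber range.

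**7. The baseline anchor.** Section 5.3 puts randomisation after the baseline measures but gives no interval. If Visit 3 is counted from baseline, any such interval lengthens the gaps in step 4 day for day.

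**The case against.** The strongest reply is that the protocol does not clearly cut the course short. Section 5 links stimulator return to completion of the intervention, and the interview sections assume that the 12 weeks are over. Sites following those passages would leave the device in place after an early Visit 3, and no session would be lost. This stands as a limit on the finding: the two statements on return conflict, and the arithmetic applies only if the flow chart is followed.

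A reader might also infer that participants in general cannot reach 36 sessions, or that Green is out of reach. Neither is supported. A prompt start with Visit 3 on target allows all 36, a day-4 start allows 35, and 27 is attainable in every case computed. The gap of about two weeks also needs the working-day window; Table 2 gives at most 11 days.

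A further tempting step is to add the pause of up to 7 days in Section 5.2.1.2. Three fewer sessions would turn 30 into 27, leaving no slack. That needs the latest start, the earliest visit, a full pause and no catch-up in one person. The same passage also pauses follow-up assessments, so the visit may move too. What remains is that it does not say how a paused assessment relates to the visit windows, including the plus or minus 3 days at Visit 2.

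The 75% shared by Green and Amber in Table 3 is settled by the session counts in the same row, so it is a wording matter. How individual counts become a trial-level rating may be in the SAP and is not raised here. The earlier timing of the 12-week outcomes carries little weight, because Section 7.3 rules out comparisons between groups.

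**Conclusion.** The concern holds in a limited form. The protocol gives Visit 3 two anchors and two windows, ties neither anchor to the start of treatment, and contradicts itself on when the stimulator goes back. For a participant seen at the early limit, this can remove about 3 to 6 of the 36 sessions under the text window, or 3 to 4 under Table 2, from a measure still divided by 36. The effective Green threshold then rises from 75% to between 82% and 90% of the sessions available.

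The result rests on return at Visit 3, evenly spaced sessions without catch-up, and baseline on the day of randomisation. The protocol does not say how many participants would be seen early, so the effect on trial-level adherence cannot be estimated. The bias is modest and always downward, it touches a progression criterion, and it is cheap to remove before sites start scheduling visits.

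**What to change.** - State one anchor and one window unit for all visits, identically in Section 5, Section 5.6 and Table 2.
- Set the Visit 3 window so that it does not open before the participant's scheduled 12-week course ends, for example 0 to +7 days from that point. If the window is counted from 12 weeks after randomisation, its opening must also allow for the 4-day start allowance; otherwise a day-4 starter could still be seen with 35 of 36 sessions possible. Use the same window in both arms so that assessment times stay comparable.
- Reconcile the flow chart with the discharge paragraph of Section 5 on stimulator return, and the pause provisions of Section 5.2.1.2 with the visit windows of Section 5.6. Which rule applies is for the trial team; the treatment course itself need not change.
- In Table 3, write Amber as 50% to below 75%, to match its own band of 18 to 26 sessions.

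The cost is wording in Sections 5, 5.2.1.2 and 5.6, Table 2, the flow chart and Table 3. The one practical downside is that Visit 3 would fall a few days later on average.
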